### Statistics

#### Sample size

The sample size mirrors the epidemiological context of a decline in the number of g-HAT cases due to the elimination efforts put in place by the WHO and partners. The PNLTHA in DRC and Guinea reported in 2019, in areas where clinical sites will be based, 50 patients were detected in the age range of 0 to 15 years old. The number of patients per age group is not critical for the pop-PK model since the model can adapt the results to the population. A proposed sample size of 35 patients reflects operational feasibility and should provide sufficient model-informed safety and efficacy under the epidemiological elimination context

of g-HAT.

Since this is not a controlled study with an active comparator, the efficacy in this paediatric study will be descriptive. A sample size of 35 patients is targeted to obtain limits of the 95% confidence interval (CI) of rates as "reasonable" as possible. With 35 patients, if no patients have the attribute of interest such as failure of treatment, the exact limits of the 95% CI would be 0% to 10%. If one patient has the attribute of interest (one failure) the 95% CI would be 0.072% to 14.92% and in the case of two failures, the 95% CI would be 0.069% to 19.16%. The upper limit would be close to 20% for two observed cases, 15% for one case and 10% for no cases observed. The expected success rate in efficacy should be approximately 95% (as large as NECT in second stage and better than pentamidine in first stage). In this case, the chance of observing no failures is 16.6%,  $\leq$ one failure is 47.2%, and  $\leq$ two failures is 74.6%. Consequently, even if a power of 80% is not reached, the chance of observing a success rate  $>94\%$  (i.e.  $\leq$ two failures out of 35 patients) is not negligible, if the expectation is correct (which is pending results of the ongoing pivotal study in adults). With regards to the safety analysis, a sample size of 35 patients gives a 95% chance of observing an event with an occurrence probability of at least 0.082. The chance of observing uncommon events ( $<1\%$ ) is 16.6%. In conclusion, a sample size of 35 patients will ascertain whether the order of magnitude of the success rate is similar to that observed in adult patients and whether common adverse events (AEs) are similar to that of observed in the adult population.

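### The 16.6% chance of seeing an adverse event with incidence below 1% does not follow from 35 patients; at a true incidence of 1% it is 29.7%, and lower for rarer events (minor correction)

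*Protocol*

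**What the plan says.** Under Statistics, Sample size, the protocol makes two numerical statements about safety with 35 patients. The first is a detection threshold: "95% chance of observing an event with an occurrence probability of at least 0.082". The second follows directly. It begins "The chance of observing uncommon events", adds in brackets that these are events below 1%, and gives 16.6%. No other incidence is named for the second statement.

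The same number appears earlier in the section for a different quantity. The efficacy part starts from this premise: "The expected success rate in efficacy should be approximately 95" (per cent). From it the protocol derives that "the chance of observing no failures is 16.6" (per cent), followed by 47.2% for at most one failure and 74.6% for at most two.

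The section closes by saying what 35 patients will establish: the order of magnitude of the success rate, and whether common adverse events resemble those in adults.

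**The concern.** The two safety sentences answer the same kind of question: how likely are 35 patients to show at least one event of a given incidence? One formula should therefore produce both figures. It produces the first but not the second. The second also matches, to three digits, a probability of a different kind at a different rate: no event rather than at least one, at 5% rather than below 1%.

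An ethics committee or regulator reads this sentence to learn how much a study of 35 children can reveal about less frequent harms, and safety is a named secondary objective. A wrong detection probability misinforms that reader, even where nothing else in the design depends on it.

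**Working it through.** **Inputs, all from the Sample size section.** n = 35. Safety threshold: incidence 0.082 for a 95% chance. Incidence named in the uncommon-event sentence: below 1%, so 0.01 is its upper bound. Expected success rate 95%, so a failure rate of 0.05.

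**Formula.** With independent patients and true incidence p, the chance of at least one event among n patients is 1 - (1 - p)^n, and the chance of none is (1 - p)^n.

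**Step 1: reproduce the figures around it.**
- Safety threshold: 1 - (1 - 0.082)^35 = 0.950. Solved the other way, p = 1 - 0.05^(1/35) = 0.0820. Both agree with the protocol.
- No failures at a 5% failure rate: 0.95^35 = 0.1661, or 16.6%. This agrees.
- At most one failure: 0.472. At most two: 0.746. Both agree.

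So the formula and n = 35 are those the protocol uses, and 16.6% is correct where it first appears.

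**Step 2: the uncommon-event figure.**
- At p = 0.01: 1 - 0.99^35 = 0.2966, or 29.7%.
- Stated: 16.6%. Difference: 29.7 - 16.6 = 13.1 percentage points; ratio 29.7 / 16.6 = 1.8.
- Chance of missing such an event entirely: 100 - 29.7 = 70.3%, against 100 - 16.6 = 83.4% implied by the text.

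**Step 3: does another reading give 16.6%?**

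| Reading, n = 35 | Chance |
|---|---|
| At least one event, p = 1%, Poisson approximation | 29.5% |
| Exactly one event, p = 1% | 24.9% |
| At least two events, p = 1% | 4.8% |
| At least one event, p = 0.5% | 16.1% |
| At least one event, p = 0.1% | 3.4% |
| At least one event, averaged evenly over p from 0 to 1% | 15.7% |

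None gives 16.6%. Solving 1 - (1 - p)^35 = 0.166 gives p = 1 - 0.834^(1/35) = 0.0052. An incidence of 0.52% would be needed, and the protocol does not state one.

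**The case against.** The strongest reply is that the sentence names a range, not 1% exactly. Within that range 29.7% is only the upper bound, and the incidence that would give 16.6%, namely 0.52%, lies inside it. An incidence of 0.5%, or an even average over the range, comes close. This stands to the extent that 29.7% must not be called the one correct value for events below 1%; it is the value at 1% and a ceiling below that. It does not rescue the printed figure. The protocol states no rate or averaging rule that leads to 16.6%, and the two natural candidates give 16.1% and 15.7%.

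The second reply concerns weight, and it stands. A reader might infer that the sample size or the safety conclusion depends on this number. The text does not support that. The protocol attributes 35 to operational feasibility in a setting where 50 patients aged 0 to 15 were detected in 2019. The closing statement is about common adverse events, for which the relevant figure is the 0.082 threshold, and that reproduces. A reader might also infer that the protocol claims more sensitivity than it has. At 1% it claims less. Only for an incidence below 0.52% would 16.6% be too high.

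Finally, a reader might infer that this is the only faulty number in the section. That does not hold either. The printed lower confidence limit for two failures, 0.069%, lies below the 0.072% printed for one failure, whereas the exact value is about 0.70%. That is a separate correction.

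**Conclusion.** The stated 16.6% is wrong as written. With 35 patients, the chance of at least one event is 29.7% at a true incidence of 1% and lower for rarer events. The gap at 1% is about 13 percentage points, in the direction of understating detection. The only assumptions are independent patients, all 35 observed for the event, and the same formula that yields the protocol's own 0.082.

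Carry-over from the no-failure probability is the most plausible origin, because 0.95^35 matches to three digits. It remains an inference, since the protocol does not show how the figure arose.

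This is a minor correction of a stated figure. On either number a 1% event would more likely be missed than seen, and neither the sample size nor the stated conclusion about common adverse events changes.

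**What to change.** Replace the sentence with: *The chance of observing at least one event with a true incidence of 1% is 29.7% (lower for rarer events).* Naming the incidence matters as much as changing the number, because a single percentage cannot describe an open range. Values for rarer events, such as 16.1% at 0.5% or 3.4% at 0.1%, may be added but are not needed.

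The cost is one sentence in the protocol's Sample size text. The design, sample size, analyses and conclusion stay as they are.

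### The sample-size conclusion says 35 patients will establish whether common adverse events are similar to adults, but its figures support only seeing an event at least once

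*Protocol*

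**What the plan says.** The Sample size section of the protocol explains 35 patients first by feasibility: "A proposed sample size of 35 patients reflects operational feasibility". It describes the efficacy analysis as descriptive because there is no active comparator. It then gives confidence limits for a generic attribute, with treatment failure as the example. For no cases, "the exact limits of the 95% CI would be 0% to 10" per cent; the upper limits for one and two cases are 14.92% and 19.16%.

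For safety it gives two figures. The first is that the sample "gives a 95% chance of observing an event with an occurrence probability of at least 0.082". The second is "The chance of observing uncommon events ( $<1\%$ ) is 16.6" per cent.

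It closes by saying that 35 patients will ascertain two things: whether the success rate is of a similar order of magnitude to that in adults, and "whether common adverse events (AEs) are similar to that of observed in the adult population". The section gives no adult adverse event rate, no limit for what counts as similar, and no power or precision for a comparison of adverse event rates.

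**The concern.** The conclusion does not follow from what precedes it. Both safety figures answer whether an event would be seen at all. The conclusion answers a different question, whether its rate resembles the adult rate, and does so with a verb of certainty. On the natural reading, the qualifier about order of magnitude attaches to the success rate only, so the adverse event half stands without a hedge.

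There is also a gap in detection. The paragraph labels events below 1% uncommon, which suggests that common starts at about 1%, yet its 95% assurance starts only at 8.2%.

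Assessing the safety profile is a secondary objective, and this sentence is the sample-size justification for it. If it stands, no cases or few cases among 35 children could later be reported as safety like that in adults, with the protocol cited in support.

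**Working it through.** **Inputs from the protocol (Sample size section):** n = 35; detection threshold 0.082 at 95%; 16.6% for events below 1%; upper limits of 10%, 14.92% and 19.16% for 0, 1 and 2 cases. **Assumed, because the protocol gives none:** adult rates of 2%, 5%, 10%, 20% and 30%, each taken as known, and a child rate of twice the adult rate.

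**1. The protocol's own figures.**
- Threshold for a 95% chance of at least one case: 1 − 0.05^(1/35) = 0.0820. This reproduces.
- Exact (Clopper-Pearson) upper limits for 0, 1 and 2 cases in 35: 10.0%, 14.92% and 19.16%. These reproduce, as does the lower limit of 0.072% for one case.
- Chance of observing an event below 1%: at a rate of exactly 1% it is 1 − 0.99^35 = 29.7%, and it falls towards zero as the rate falls. The stated 16.6% does not describe this range. It equals 0.95^35 = 0.166, the chance of no failures that the same section gives under a 95% success rate. Read as a detection chance, it would fit only a rate of about 0.52%.
- Lower limit for two cases: 0.70%, where the protocol has 0.069%.

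**2. Chance of at least one case, 1 − (1 − p)^35.**

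| True rate p | Chance of at least one case |
|---|---|
| 1% | 29.7% |
| 2% | 50.7% |
| 3% | 65.6% |
| 5% | 83.4% |
| 8.2% | 95.0% |
| 10% | 97.5% |

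The stated assurance therefore does not cover rates from 1% to 8.2%.

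**3. Can 35 patients tell a doubled rate from the adult rate?** For each assumed adult rate a, find the smallest count whose 95% interval lies wholly above a, then take the binomial probability of reaching that count when the child rate is 2a. Both interval types are shown: the section uses exact limits, and the Efficacy analysis section uses Jeffreys.

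| Adult rate → child rate | Cases needed (exact / Jeffreys) | Probability that the interval excludes the adult rate (exact / Jeffreys) |
|---|---|---|
| 2% → 4% | 4 / 3 | 5% / 16% |
| 5% → 10% | 6 / 5 | 13% / 27% |
| 10% → 20% | 8 / 8 | 40% / 40% |
| 20% → 40% | 13 / 12 | 69% / 80% |
| 30% → 60% | 17 / 16 | 94% / 97% |

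**4. The same point from interval widths.** The exact intervals for 1, 2, 3 and 4 cases in 35 are 0.07–14.9%, 0.7–19.2%, 1.8–23.1% and 3.2–26.7%. An adult rate of 5% and a doubled rate of 10% both lie inside all four.

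**5. Sensitivity to taking the adult rate as known.** Against an assumed adult sample of 100 to 1,000, two-sided 5% power for a doubling (two-proportion comparison) is 22–32% from 5% and 35–49% from 10%. The conclusion is the same.

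**The case against.** The strongest reply is that this is one loose verb in a feasibility-driven paragraph. To ascertain whether rates are similar does not declare that they are. The primary objective is pharmacokinetic, the safety endpoints are occurrences of events, and no hypothesis, margin or decision rule rests on the sentence. The limits are largely disclosed already, including the 10% upper limit for no cases and the 8.2% threshold. Common is never defined, and could mean events of about 8% or more, since the conclusion follows that figure.

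Much of this is fair, and it limits the point. If common means 8.2% or more, the detection gap disappears. The similarity problem remains: a doubling from 8.2% to 16.4% would be shown by the exact interval with a probability of only 35%. Disclosing the limits does not help when the closing sentence sets them aside.

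Two stronger readings are tempting and are not supported. A reader might infer that the trial would miss most common events. It would not: only rates below about 2% are more likely missed than seen, and averaged evenly over 1% to 10% the chance of at least one case is 79%. A reader might also infer that the protocol's figures themselves show that a doubling would go unnoticed. They do not: the protocol computes no such probability, and the result depends on adult rates assumed here.

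**Conclusion.** The safety half of the conclusion is wrong as written. The design gives a 95% chance of seeing at least one case of an event with a rate of 8.2% or more. It does not establish that common adverse event rates are similar to those in adults. For assumed adult rates of 2% to 10%, a doubled child rate would be shown with a probability of only 5% to 40%, depending on the rate and the interval.

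This does not extend to very frequent events: from an adult rate of 20% upwards the probability is about 69% (exact) or 80% (Jeffreys), and higher beyond that. The result rests on n = 35, an adult rate treated as known, and a twofold difference as the yardstick. Reading common as 1% and above is an inference from the section's label for uncommon events.

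The 16.6% figure is a separate error that needs none of these assumptions. The sample size itself is a feasibility limit and is not in question.

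**What to change.** Replace the safety half of the concluding sentence with wording such as: *35 patients give a 95% chance of observing at least one case of an AE with an incidence of at least 8.2%. AE rates will be described with 95% CIs beside the adult rates, and similarity to adults will not be concluded. No event in 35 patients is compatible with a true rate of up to 10% (exact).*

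In the same section, correct the chance of observing events below 1% from 16.6% to at most 29.7%, reached at a rate of 1%. The lower limit for two cases (0.70%, not 0.069%) can be corrected in the same edit.

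The cost is wording only. Sample size and conduct do not change. The downside for the sponsor is a less favourable safety statement.

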#### Pharmacokinetic analysis

The first validation of the weight-based exposure model will be done using data from the first six paediatric patients. The bioavailability (concentration) obtained for each paediatric patient will be compared to the initial model predicted. This will allow assessment of whether exposure is acceptable and, if required, to adjust the exposure for subsequent patients by changing the weight band for a given exposure. If the concentration is, on average, too small or too large, the weight band will be adapted.

The complete data collected from the included patients at the end of study will be included in the model, to complete the validation of the predicted model.

A final validation of the pop-PK model of acoziborole will use the pooled data from adults and adolescents with g-HAT included in the DNDi-OXA-02-HAT pivotal Phase II/III study and paediatric patients from this current study. All observed data will be used to confirm or adjust (if needed) the prediction of the efficacy and dose for each formulation and bodyweight, to estimate pop-PK parameters in paediatric patients, and to determine the related variability. The observed mean concentration and its 95% CI will be calculated to assess the compatibility, on average, of observed data with predicted data.

Acoziborole PK parameters will be calculated using a noncompartmental analysis method to derive the following parameters:  $C_{max}$ ,  $T_{max}$ ,  $AUC_{0-96h}$ , and  $AUC_{0-\infty}$ .

#### Efficacy analysis

Efficacy will be assessed according to the algorithm for treatment outcomes at 6 and 12 months post-treatment.

The efficacy analysis will estimate the success rate at 12 months of follow-up. The 95% Jeffreys CI of the estimate will be provided. The success rate at 12 months in adults will be used as a yardstick.

Changes in the rate of success outcomes over time will be studied descriptively.

Time to proven relapse will be analysed in each cohort using the Kaplan-Meier approach to estimate, at each follow-up visit, the cumulative rate of proven failures. Patients lost to follow-up will be censored at the last available visit unless the outcome at that visit was failure.
